
Study Size
	
The study size was estimated for the primary outcome of live birth (measured as LBR, CLBR and MC-CLBR) based on publicly available annual reports from the Danish and Swedish IVF registers and the previous feasibility study conducted by PPD .
 
As each woman to be included in the analysis will have at least one stimulation cycle, the number of women having a stimulation cycle with a study drug is the limiting factor for the study size. Thus, the study size was estimated based on the number of women and using the outcome measure of MC-CLBR.
 
The anticipated approximate maximum number of women who have initiated a stimulation cycle with a study drug, and will be available for the comparison of rhFSH-alpha reference product and HP-hMG products (study period starting in 2010), is as follows:
 
 • 19,000 women in rhFSH-alpha reference product cohort and 12,000 women in HP-hMG cohort, in Denmark • 18,000 women in rhFSH-alpha reference product cohort and 17,000 women in HP-hMG cohort, in Sweden 
For the comparison of rhFSH-alfa reference product and rhFHS-alfa biosimilar products (study period starting in 2014), the corresponding numbers are the following:
 
 • 14,000 women in rhFSH-alpha reference product cohort and 3,000 women in rhFSH-alpha biosimilar product cohort, in Denmark • 11,000 women in rhFSH-alpha reference product cohort and 10,000 women in rhFSH-alpha biosimilar product cohort, in Sweden 
The conservative minimal detectable difference between the study groups was investigated to show the minimal differences in primary outcomes that can be detected in this study. The minimal detectable difference was calculated by using the measure of association in this study: odds ratio (OR) and its corresponding 95% confidence interval (CI). The minimal detectable difference is the difference in the outcome rates between the study cohorts that will yield an OR whose lower 95% CI is above 1.
 
To take into account the effect the study inclusion and exclusion criteria, a crude assumption that 75% of the women are eligible for the study. With this assumption, the anticipated study size will be able to show any differences of 1.5 percentage point (% point) in primary outcomes between the rhFSH-alfa reference product and HP-hMG study cohorts, in both Denmark and Sweden. For comparison of rhFSH-alfa reference

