9.1.2.1 Primary

The primary outcome of this study is live birth. It is defined generally as the complete expulsion or extraction from a woman of a product of fertilization, after 22 completed weeks of gestational age; which, after such separation, breathes or shows any other evidence of life, such as heartbeat, umbilical cord pulsation or definite movement of voluntary muscles, irrespective of whether the umbilical cord has been cut or the placenta still attached or not (16).

Information on live birth will be obtained from the medical birth register in each country and the IVF register in Sweden. Only live births that can be linked to a given IVF/ICSI stimulation cycle included in the study will be considered. The live birth of multiples will be counted as one live birth in this study.

For the assessment of the primary objective and secondary objective 4, the different measures of live birth are defined as follows:

- LBR is the probability of a live birth after one initiated stimulation cycle, considering fresh embryo transfer.
- CLBR is the number of live births per initiated stimulation cycle, considering all fresh and subsequent frozen embryo transfers linked to that stimulation cycle and counting all live births from the same transfers.
- MC-CLBR is the probability of a live birth in up to five stimulation cycles, considering all fresh and subsequent frozen embryo transfers linked to each of those stimulation cycles, until the first live birth occurs.
- TTLB is the time (in number of cycles) until live birth in up to five stimulation cycles, considering all fresh and subsequent frozen embryo transfers linked to each of those stimulation cycles, until the first live birth occurs.

For the calculation of the above measures, refer to Section 9.7.3.3 (Table 7).

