9.6 Data Management

All study permit approvals and access to the study data will be applied for by PPD . Application for access to individual-level data for scientific research follows a standard application procedure at the Danish and Swedish authorities. For Denmark, pseudonymized individual-level data are placed at a secure, remote server of the Danish Health Data Authority. All data analyses using the linked register data must be conducted at the server of the authority by PPD staff personally authorized by the authority under the authorisation held by PPD Solutions Denmark A/S. No other PPD staff will have access to the secure server environment. For Sweden, data from each register will be extracted by the respective register holder and delivered to PPD as pseudonymized individual-level data without unique personal identification numbers. The researchers at PPD in Denmark and Sweden will thus have access to data where individuals cannot be directly identified.

Before PPD can access the data, the data holders have collected and managed data according to their own standards. As the data contained with the national registers have been collected independently of the current study, the data collection process could not affect the research question. Once the data can be accessed, PPD will start processing the data. Each country will perform analyses with individual-level data separately as described in Section 9.7. SAS v9.4 (SAS Institute, Inc. Cary, North Carolina) or R v3.6.5 or higher (R Foundation for Statistical Computing, Vienna, Austria) languages will be used in data management for creating the analysis database, and in statistical analysis for creating tabulations and graphics, as well as in all statistical modelling. The source code of data management and data analyses is kept for inspection for five years after completion of the study (latest of final study report or first publication of study results).

According to PPD standard operating procedure, only selected study staff have rights to files and directories that contain individual-level data stored on site. Access to the individual-level study data cannot be given to any third parties; only aggregated results will be presented to the Sponsor or otherwise published. The study data cannot be used for other purposes than described in this protocol. All requests to use the study data for other purposes must be subjected to appropriate data permit processes.

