9.7.3.5 Time-to-Live Birth Analysis

TTLB (secondary objective 4) will be analyzed restricting to women who initiated their first-ever stimulation cycle during the study period. As per study design, only the first five stimulation cycles (including all cycles of fresh or frozen embryo transfers) with the same study drug will be considered. The stimulation cycle rank number will be employed as the unit of time. Women will be followed until the first delivery with at least one live birth linked to treatment with the drug of interest, the sixth stimulation cycle, switch to another drug used for COS, diagnosis of breast, ovarian or uterine cancer, death, emigration (Denmark only) or end of study, whichever occurs first.

To estimate the TTLB in the original and IPTW-weighted study cohorts, survival analysis will be performed with the Kaplan-Meier method to estimate the time to the first live birth, expressed as the rank number of the stimulation cycle with the given study drug. The resulting Kaplan-Meier plots together with the estimated mean (with 95% CI) and median (with 95% CI) time-to-events will be presented.

For the comparison of the study cohorts, the time-to-live birth rate ratios adjusted for confounding factors, will be estimated by taking into account the IPTWs and using Cox proportional hazards regression model. The Cox model will be weighted with the IPTWs, and any variables included in the PS that are still unbalanced after weighting will be included as covariates for the Cox model. Additionally, the Cox model may be used to adjust the rate ratios for any other potential covariates that are assessed after the start of the stimulation cycle and hypothesized to be associated with the given study outcomes (see Table 1 in Section 9.3.2).

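### Time-to-live birth uses a Cox model on five cycle ranks, so every event is tied and the tie method decides which ratio is reported

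*Protocol*

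**What the plan says.** Section 9.1.2.1 of the protocol defines the outcome in cycles: "TTLB is the time (in number of cycles) until live birth in up to five stimulation cycles". Section 9.7.3.5 repeats this for the analysis ("The stimulation cycle rank number will be employed as the unit of time") and limits follow-up: "only the first five stimulation cycles (including all cycles of fresh or frozen embryo transfers) with the same study drug will be considered". A birth from a frozen transfer counts under the stimulation cycle it is linked to, so event time can only be 1, 2, 3, 4 or 5.

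For the comparison, the ratios "will be estimated by taking into account the IPTWs and using Cox proportional hazards regression model". Table 6 calls the result an adjusted live birth rate ratio. Neither place says which ratio is meant, and no tie method or discrete-time form is named. Section 9.6 allows "SAS v9.4 (SAS Institute, Inc. Cary, North Carolina) or R v3.6.5 or higher". Countries are analysed separately, and section 9.7.3 leaves further detail to an SAP that is not at hand.

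**The concern.** The Cox partial likelihood is built for event times that are rarely shared. Here all events share five times, with hundreds to thousands at most of them. At that level of tying, the usual tie options are not small numerical variants of one estimate. They estimate different measures of effect: a probability ratio, a hazard ratio or an odds ratio.

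The study hypothesises superiority, and one of its motivating studies (section 7) reports a hazard ratio of 1.10 (95% CI 1.04 to 1.16). When effects are that close to 1, a reader needs to know which measure the TTLB ratio is and whether its interval belongs to it.

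**Working it through.** The protocol gives no event count, power or effect size for TTLB, so there is no figure to reproduce. The check uses expected counts.

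**Inputs from the protocol**
- Women, reference vs comparator (abstract and Table 2): "19,000 women in rhFSH-alpha reference product cohort and 12,000 women in HP-hMG cohort, in Denmark"; "14,000 women in rhFSH-alpha reference product cohort and 3,000 women in rhFSH-alpha biosimilar product cohort, in Denmark"; Sweden, biosimilar comparison, 11,000 and 10,000.
- 75% eligible (section 9.5), giving 14,250/9,000, 10,500/2,250 and 8,250/7,500.
- Hazard ratio 1.10 vs hMG. Relative risk 0.82 for biosimilars, or 1/0.82 = 1.22 inverted (section 7).

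**Assumptions not in the protocol**
- Comparator live birth per cycle falls over the five ranks from 15% to 11%, from 25% to 17%, or from 35% to 23%. Cumulative rates are then about 30%, 45% and 57%, around the 50% used in section 9.5.
- 65% of women without a birth start the next cycle.
- Proportional hazards hold, with no covariates and no weights.

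**Step 1: are events tied?** Denmark HP-hMG, 25% scenario, hazard ratio 1.10: about 6,116, 2,696, 1,213, 556 and 259 births at ranks 1 to 5. The smallest group in any run (Denmark biosimilar, rank 5) still has over 100.

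**Step 2: what each method estimates.** At rank j let n1, n0 be at risk and d1, d0 have births. The Breslow score is the sum over ranks of d1 − (d1 + d0) × n1·e^β / (n1·e^β + n0). If d1/n1 = θ × d0/n0 at every rank, then d1 + d0 = (d0/n0)(θ·n1 + n0). Each term is zero at e^β = θ, so Breslow returns the per-cycle probability ratio exactly.

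For 30% vs 27% at rank 1:
- probability ratio: 0.30/0.27 = 1.111
- grouped-time hazard ratio: ln(0.70)/ln(0.73) = 1.133
- odds ratio: (0.30/0.70)/(0.27/0.73) = 1.159

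Solved over five ranks, with rates falling 7% per rank, the methods give Breslow 1.111, Efron 1.13 and exact discrete about 1.16.

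**Step 3: size at an assumed grouped-time hazard ratio.**

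| Comparator rank-1 rate | True HR | Breslow | Efron | Exact discrete |
|---|---|---|---|---|
| 15% | 1.10 | 1.092 | 1.100 | 1.109 |
| 25% | 1.10 | 1.086 | 1.099 | 1.116 |
| 35% | 1.10 | 1.080 | 1.098 | 1.124 |
| 15% | 1.22 | 1.200 | 1.219 | 1.241 |
| 25% | 1.22 | 1.186 | 1.218 | 1.258 |
| 35% | 1.22 | 1.171 | 1.216 | 1.280 |

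Hand check, 25% row at 1.10: p1 = 1 − 0.75^1.10 = 0.2713, so the rank-1 probability ratio is 1.085 and the odds ratio 1.117. A complementary log-log model returns 1.100 and 1.220 throughout.

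**Step 4: the interval under Breslow.** Sweden biosimilar, 25% scenario, hazard ratio 1.05, rank 1: d0 = 0.25 × 7,500 = 1,875 and d1 = (1 − 0.75^1.05) × 8,250 = 2,151.
- Breslow variance: 1/2,151 + 1/1,875 = 0.000998, SE 0.0316.
- Variance of a log probability ratio: the same minus 1/8,250 and 1/7,500 = 0.000744, SE 0.0273.

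The Breslow interval is thus about 16% too wide at rank 1 (0.0316/0.0273) for the quantity it estimates.

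**Step 5: can it matter?** Hazard ratio 1.05, model-based 95% intervals:
- Sweden biosimilar, 25%: Breslow 1.043 (0.996 to 1.093), Efron 1.050 (1.002 to 1.099)
- Sweden biosimilar, 35%: Breslow 1.040 (0.998 to 1.084), Efron 1.049 (1.007 to 1.093)
- Denmark HP-hMG, 15%: Breslow 1.046 (0.997 to 1.097), Efron 1.050 (1.001 to 1.101)

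At 1.10 no run crossed 1. The closest was Denmark biosimilar, 15%: Breslow 1.092 (1.005 to 1.186). TTLB is limited to women whose first-ever cycle falls in the study period, so actual cohorts will be smaller than these.

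**The case against.** The strongest reply is that Breslow is not wrong here. Time is the cycle itself, the protocol speaks of live birth rates, and step 2 shows that Breslow recovers the ratio of per-cycle rates exactly. A reader might infer that Breslow is biased toward 1 and loses 8% to 19% of the log effect at a hazard ratio of 1.10. That holds only against a grouped-time hazard ratio, which the protocol never names as its target. This part of the reply stands: the gap is between measures, not an error in one of them.

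Second, the protocol does not choose Breslow, Efron is within about 0.004 of the grouped hazard ratio, and a tie option is a detail an SAP may settle. This stands in part. A missing option alone would be no finding. But the protocol itself fixes both the five-value time scale and the Cox model, and that pairing lets the option select the measure.

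Third, a reader might infer that Denmark and Sweden will report non-comparable ratios because packages differ in their defaults. The documents do not support this. They give no default tie handling, do not assign different packages to the two countries, and expect the same type of analysis in both.

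Fourth, the crossings in step 5 use model-based variance without weights. Robust variance by woman, natural in a weighted analysis, would largely repair the Breslow interval. That also stands and limits the practical harm.

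**Conclusion.** The point holds, at modest size. Section 9.7.3.5 pairs a time scale of five values with a Cox model, every event is tied, and the resulting TTLB rate ratio may be a probability ratio, an approximate hazard ratio or an odds ratio. At an assumed hazard ratio of 1.10, Breslow and Efron differ by 0.008 to 0.018. At 1.22 they differ by up to about 0.045, and exact discrete ties reach 1.28.

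The direction does not reverse in any scenario. TTLB is a secondary objective, and the planned meta-analysis covers only the primary objective. Significance can change for an effect near 1.05 if Breslow is used with model-based variance. At 1.10 that was not seen at the planned cohort sizes, though one lower limit was only 1.005. A reader might conclude that a Cox model on cycle rank is unusable; the Efron results do not support that.

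All sizes rest on the assumed per-cycle rates and return rate, since the protocol gives neither. That all events are tied, and that the methods target different measures, does not depend on them.

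**What to change.** In both countries, replace the Cox model for TTLB with an IPTW-weighted discrete-time model on cycle rank, with rank indicators and robust variance clustered by woman. Name the link and the measure it yields: complementary log-log for a hazard ratio, or log for a per-cycle live birth probability ratio. Use that name in Table 6 and section 9.7.3.5.

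If Cox is kept, specify Efron ties with robust variance in both countries. Do not offer exact discrete ties unless the result is labelled an odds ratio.

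The cost is a change of wording in the protocol and SAP, made before results are seen. It needs no new data.

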9.7.3.6 Stratified Analysis

For the stratified analysis, the study population will be stratified into groups based on their baseline characteristics of age (<35 years old vs. ≥ 35 years old) and use of GnRH agonist or antagonist protocol. The stratified analysis will be performed for the following outcome measures: LBR, CLBR, MC-CLBR, CPR, CCPR, OPR, COPR and OHSS, and for the number of oocytes retrieved and the number of utilizable embryos per initiated stimulation cycle and per oocyte retrieval cycle. Rates and adjusted odds ratios will be estimated as described for each outcome in Sections 9.7.3.3 and 9.7.3.4.

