and after adjustment on the main confounders. Results showed significantly higher live birth in (1) the total population (adjusted hazard ratio (HR)=1.10, 95% confidence interval (CI): 1.04-1.16) and with GnRH agonists (adjusted HR=1.13, 95% CI: 1.07-1.19); (2) higher ongoing pregnancy in the total population (adjusted HR=1.10, 95% CI: 1.04-1.16) and with GnRH agonists (adjusted HR=1.13, 95% CI: 1.07-1.19); and (3) higher clinical pregnancy in the total population (adjusted HR=1.10, 95% CI: 1.05-1.14) and with GnRH agonists (adjusted HR=1.12, 95% CI: 1.07-1.17)). Results remained significant for all the 3 outcomes listed above in the analysis per first cycle and completed cycles. This supports the hypothesis that differences observed at the purity, consistency and molecule level in respect to glycosylation and other biological characteristics may have also important clinical implications, especially in the context of the GnRH agonist protocol.

rhFSH-alfa reference product and rhFSH-alfa biosimilars

rhFSH-alfa biosimilar preparations have been approved in Europe, as well as in other countries such as, but not limited to, Russian, India, China, Korea, and Argentina. Two rhFSH-alfa biosimilar products are now available on the European Union (EU) market based on the European Medicines Agency's (EMA) guideline for biosimilars approval (Ovaleap®, authorized since 2013; Bemfola®, authorized since 2014) (4).

Approval of biosimilars has the main objective to guarantee treatment accessibility to all the patients in all the markets, in an ideal case, due to lower price of the product with the same safety and efficacy as the reference product (13).

In Europe, according to the guideline of EMA, the Marketing Authorization application dossier of a biosimilar medicinal product shall provide a full quality dossier together with data demonstrating comparability with the reference medicinal product by using appropriate physical-chemical and in vitro biological tests, non-clinical studies and clinical studies (14). Until now, biosimilarity of new rhFSH-alfa preparations have been demonstrated with Phase III clinical trials powered to detect non-inferiority on the number of oocytes retrieved when compared with the reference preparations.

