As stated above, usually live birth is reported in pivotal clinical trials (CTs) as a secondary outcome and other meaningful clinical outcomes, including ongoing pregnancy and clinical pregnancy, are usually only partially reported in CTs. Moreover, there is scarcity of data in terms of cumulative pregnancy or live birth across all cycles. The overarching reason for this research gap is the requirement of an extensive study follow-up period to evaluate such endpoints. Therefore, use of real-world data (RWD) can be an efficient way to address these types of outcomes, as patient data are collected longitudinally, often over a long period of time, in routine practice. Moreover, the clinical evidence generated based on RWD (so-called real-world evidence [RWE]) and the associated cost of treatment, is valuable for health-economic evaluations. RWE provides unique evidence for healthcare decision makers from different sectors (private or government) to make their decisions, which could benefit patient access and reduce healthcare burden (19).

Study rationale

The hypothesis tested in this study is that there are possible differences in effectiveness and safety outcomes between rhFSH-alfa reference product and urinary gonadotropins or rhFSH-alfa biosimilar products, with a beneficial effect of rhFSH-alfa reference product in terms of meaningful clinical outcomes.

With the long-term market use of rhFSH-alfa reference and urinary products, and the increased use of rhFSH-alfa biosimilar products, it is important to assess this hypothesis in the routine clinical practice setting. This will be achieved by comparing the effectiveness, and safety, of rhFSH-alfa reference product vs. highly purified (HP-)hMG or rhFSH-alfa biosimilar products, in different GnRH down-regulation regimens, regarding (cumulative) live birth and other effectiveness and safety outcomes that would be relevant for physicians, and most importantly for patients.

8 Research Question and Objectives

This study hypothesizes that controlled ovarian stimulation (COS) with rhFSH-alfa reference product is superior to COS with HP-hMG or rhFSH-alfa biosimilar products with respect to effectiveness and safety outcomes among women undergoing IVF/ICSI treatment in routine clinical practice.

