PS weighting and evaluation of its success will be done separately per each analysis set (see Section 9.7.1) as covariate balance is not automatically the same in the analysis sets that include data from slightly varying time periods and thus have may have slightly varying set of data included. Also, for stratified analyses, PS weighting and evaluation of its success will be re-done as covariate balance is not automatically maintained in the sub-groups that are created by the stratification.

In addition, other PS implementation methods, such as matching or stratification, may be considered in case the received data does not support for using IPTW approach, for any reason.

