9.7.3.4 Adjusted Odds Ratios

For the comparison of the study cohorts, the ORs (with 95% CI), adjusted for confounding factors, will be estimated by taking into account the IPTWs and using statistical modelling, such as regression analysis or general estimating equations. To estimate the adjusted ORs, the statistical model will be weighted with IPTWs and will include as covariates any variables that were used in the PS but are still unbalanced between the study cohorts after weighting. Statistical models may also be used to additionally adjust the ORs for any other potential covariates that are assessed after the initiation of the IVF/ICSI stimulation cycle and hypothesized to be associated with the given study outcomes (see Table 1 in Section 9.3.2).

For the statistical models, the following study outcomes will be considered as binary outcomes analyzed per fresh embryo transfer: live birth (*i.e.*, a primary objective outcome), clinical pregnancy and ongoing pregnancy (*i.e.*, a subset of secondary objective 1 outcomes). For the statistical models, the following study outcomes will be considered as binary outcomes analyzed per woman: MC-CLBR (*i.e.*, a primary objective outcome) will be analyzed as a binary outcome per woman in statistical models.

For the statistical models, the following study outcomes will be considered as binary outcomes analyzed per clinical pregnancies following fresh or frozen embryo transfer: pregnancy loss (secondary objective 5) and multiple pregnancy (secondary objective 6). Cycle cancellation (secondary objective 7) and OHSS occurrence (secondary objective 8) will be analyzed as binary outcomes per initiated stimulation cycle. Implantation (secondary objective 3) will be analyzed as an ordinal categorical outcome per fresh or frozen embryo transfer.

For the statistical models, the following study outcomes are considered as counts analyzed per initiated stimulation cycle: cumulative live birth (*i.e.*, a primary objective outcome), cumulative clinical pregnancy and cumulative ongoing clinical pregnancy (*i.e.*, a subset of secondary objective 1 outcomes). Also the following study outcomes are considered as counts in statistical models and

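### The age and GnRH strata are analysed separately, with no estimate of whether the product effect differs between them, and Table 6 and Section 9.7.3.6 disagree on which measures are stratified

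*Protocol*

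**What the plan says.** Section 9.7.3.6 forms strata by "age (<35 years old vs. ≥ 35 years old) and use of GnRH agonist or antagonist protocol". It names eight rate measures, "LBR, CLBR, MC-CLBR, CPR, CCPR, OPR, COPR and OHSS", and adds the "number of oocytes retrieved and the number of utilizable embryos per initiated stimulation cycle and per oocyte retrieval cycle". The method within strata is one sentence: "Rates and adjusted odds ratios will be estimated as described for each outcome in Sections 9.7.3.3 and 9.7.3.4". Section 9.7.3.4 supplies the interval: "the ORs (with 95% CI), adjusted for confounding factors, will be estimated by taking into account the IPTWs". Section 9.7.3.1 makes the strata separate fits: "for stratified analyses, PS weighting and evaluation of its success will be re-done".

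Three other places bear on why the strata exist:

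- Section 7 (reference product and hMG) concludes from a German real-world study that product differences "may have also important clinical implications, especially in the context of the GnRH agonist protocol".
- The study rationale in Section 7 says the products will be compared "in different GnRH down-regulation regimens, regarding (cumulative) live birth and other effectiveness and safety outcomes".
- ENCePP checklist item 8.1, on effect modifiers, is answered yes and points to Sections 9.7.3.6 and 9.7.3.9.

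Table 6 marks a stratified analysis for LBR, CLBR, CPR, OPR, CCPR, COPR and oocytes retrieved (on both denominators). It marks none for MC-CLBR, OHSS or utilizable embryos.

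**The concern.** The background suggests that the product effect may be larger under agonist protocols. That is a question about a difference between two effects. The stated method gives each effect separately and never sets one against the other. The only heterogeneity assessment in the protocol is between countries, for the meta-analysis (Section 9.7.3.8).

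Without a planned contrast, a reader of the results has only two CIs to compare. If one excludes 1 and the other does not, the natural reading is a regimen-specific or age-specific effect. That pattern arises readily when the true effect is the same in both strata, because each stratum holds only part of the data.

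The mismatch between the two lists is a separate matter. Whether a primary measure gets a subgroup analysis depends on which part of the protocol is followed.

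**Working it through.** **Inputs.** Section 9.5 gives the numbers of women (reference/comparator). For HP-hMG they are 19,000/12,000 in Denmark and 18,000/17,000 in Sweden. For biosimilars they are 14,000/3,000 in Denmark and 11,000/10,000 in Sweden. It also assumes 75% eligibility and a comparator MC-CLBR of 50%, and calls a 5% difference clinically meaningful, which is 2.5 points at a 50% rate (Table 4). Stratum shares are not given. I assume 50:50 and show 25:75 as well.

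**The plan's own figure.** A difference is called detectable when the lower 95% limit of the OR is above 1, that is, ln(OR) = 1.96 × SE, with SE² = 1/[n0·p0(1−p0)] + 1/[n1·p1(1−p1)]. At 75% of the cohorts the smallest such differences are 1.32 and 1.22 points (HP-hMG, Denmark and Sweden) and 2.28 and 1.57 points (biosimilars, Denmark and Sweden). Taken up to the next step of Table 3 these are 1.5, 1.5, 2.5 and 2.0, as the protocol states. In a half-size stratum they become 1.87, 1.72, 3.22 and 2.22 points.

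**Discordance under one common effect.** Worked for Denmark, HP-hMG, 50:50:

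- Each stratum has 19,000 × 0.75 × 0.5 = 7,125 and 12,000 × 0.75 × 0.5 = 4,500 women.
- ln(OR) for 52.5% against 50% is ln(0.525/0.475) = 0.1001.
- SE² = 1/(4,500 × 0.25) + 1/(7,125 × 0.249375) = 0.001452, so SE = 0.0381.
- Power per stratum = Φ(0.1001/0.0381 − 1.96) = Φ(0.667) = 0.748.
- Chance that exactly one CI excludes 1 = 2 × 0.748 × 0.252 = 0.377.

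With unequal strata the formula is pa(1−pb) + pb(1−pa).

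**Power of the between-stratum contrast.** Take a 2.5-point effect in one stratum and none in the other. For Denmark, HP-hMG, the stratum without effect has SE² = 1/(4,500 × 0.25) + 1/(7,125 × 0.25) = 0.001450. The SE of the difference in log ORs is √(0.001452 + 0.001450) = 0.0539. Power = Φ(0.1001/0.0539 − 1.96) = 0.46.

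| Comparison | Power per stratum, 50:50 | Discordant, 50:50 | Discordant, 25:75 | Contrast power, 50:50 |
|---|---|---|---|---|
| Denmark, HP-hMG | 0.748 | 38% | 53% | 46% |
| Sweden, HP-hMG | 0.817 | 30% | 48% | 53% |
| Denmark, biosimilar | 0.331 | 44% | 48% | 19% |
| Sweden, biosimilar | 0.601 | 48% | 58% | 35% |

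With no effect in either stratum, discordance is 2 × 0.05 × 0.95 = 9.5%. A test on the ratio of ORs errs 5% of the time whatever the size of the common effect.

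**Size of the set.** Section 9.7.3.6 lists 8 rates plus 2 counts on 2 denominators, so 12 measures. With 4 strata, 2 comparators and 2 countries that is 192 stratum estimates. Table 6 marks 6 rates plus oocytes on 2 denominators, so 8 measures and 8 × 4 × 2 × 2 = 128 estimates. The proposed ratios number 12 × 2 factors × 2 comparators × 2 countries = 96 on the longer list.

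**The case against.** The strongest reply is that the protocol defers further detail to a SAP (Sections 9.7 and 9.7.3), that a between-stratum contrast is commonly specified there, and that separately weighted fits do not rule one out. This stands against any claim that effect modification will never be tested: all that can be said is that this protocol specifies no such comparison.

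It is also fair that Section 9.7.3.6 speaks of estimation and sets no alpha, test or decision rule. A reader might infer testing of every stratum at full alpha, but that is only an inference from the 95% CIs. Nor does the protocol say it will claim superiority from a stratum. No listed objective asks whether the effect differs by regimen, and regimen-specific estimates do answer the wording of the study rationale in part.

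A reader might further infer that the German study found an effect under agonists and none under antagonists. Section 7 reports hazard ratios for live birth of 1.10 overall and 1.13 under agonists, and no antagonist result, so that contrast is not documented.

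Finally, the contrast has low power, and 96 ratios would yield about 96 × 0.05 = 4.8 exclusions of 1 by chance. Both are true and limit what the fix can deliver. They do not make side-by-side CIs a better guide.

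None of this touches the mismatch between Table 6 and Section 9.7.3.6.

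**Conclusion.** The point holds in two parts. First, the stated method omits the one estimate that addresses the GnRH-dependent effect raised in the rationale. Reading the stratum CIs side by side instead would suggest a difference that does not exist in about 30% to 48% of cases, given a common 2.5-point effect and a 50:50 split. Second, Table 6 and Section 9.7.3.6 contradict each other on three outcomes, one of them primary.

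The stronger statement that a spurious subgroup finding is likely is not supported for a single measure, comparator and country when there is no effect: there the chance of discordance is 9.5%.

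The percentages rest on assumed stratum shares, a 50% comparator rate, and cohort counts that are not reduced for the restriction of MC-CLBR to women starting their first-ever cycle or for precision lost to weighting. Lower power moves the discordance figures but does not remove the problem.

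**What to change.** 1. In Section 9.7.3.6, for each stratified measure, add the ratio of the two stratum ORs (or of the corresponding effect ratios where Section 9.7.3.4 models counts) with its 95% CI. For per-cycle measures, allow for women with cycles in both strata. Label the stratified results exploratory, and state that any claim of a different effect by age or GnRH protocol rests on this ratio.
2. Make Table 6 and Section 9.7.3.6 list the same stratified measures, with an explicit decision on MC-CLBR, OHSS and utilizable embryos.

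The cost is small: the ratios use stratum estimates already planned, and the rest is wording. The downside is imprecision, with power of about 19% to 53% for a 2.5-point effect confined to one stratum at a 50:50 split, lowest for the Danish biosimilar comparison. The text should therefore add that a ratio whose CI includes 1 is not evidence of equal effects, and that isolated exclusions of 1 among up to 96 ratios need caution.
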